I assure the HIC that the principal investigator and all members of the research team are qualified by education, training, licensure and/or experience to assume participation in the conduct of this research trial. I also assure that the principal investigator has departmental support and sufficient resources to conduct this trial appropriately.

[name]
Chair Name (PRINT) and Signature

3/8/16
Date

Emergency Medicine
Department

YNHH Human Subjects Protection Administrator Assurance Statement

Required when the study is conducted solely at YNHH by YNHH health care providers.

As Human Subject Protection Administrator (HSPA) for YNHH, I certify that:

- I have read a copy of the protocol and approve it being conducted at YNHH.
- I agree to notify the IRB if I am aware of any real or apparent institutional conflict of interest.
- The principal investigator of this study is qualified to serve as P.I. and has the support of the hospital for this research project.

YNHH HSPA Name (PRINT) and Signature

Date

SECTION V: RESEARCH PLAN

1. **Statement of Purpose:** State the scientific aim(s) of the study, or the hypotheses to be tested. The **specific aims** of this proposed study are:

Aim 1. To conduct a fully powered factorial randomized trial of **1056** adult smokers to test the efficacy of 4 key components of ED-initiated tobacco treatment: MI, NRT, QL referral, and SMS texting.

Aim 2. To identify the most efficacious components of our intervention, within fixed constraints of cost effectiveness and feasibility/acceptability to providers and subjects.

Aim 3. To lay the groundwork for a future randomized trial testing the previously identified components, delivered as a package, against a control arm in a new cohort of adult ED smokers.

Our associated **hypotheses** are:

1. At 3 months, at least 1 intervention component will yield a biochemically verified tobacco abstinence rate at least 5% greater than in the control condition.
2. At 3 months, at least 1 intervention will be cost-effective, using a societal perspective.
3. At 3 months, at least 1 intervention will be acceptable and feasible to providers and subjects.

In Year 4, we will propose a randomized clinical trial to test, as a package, the components identified as both clinically effective and cost-effective.

2. **Background:** Describe the background information that led to the plan for this project. Provide references to support the expectation of obtaining useful scientific data.

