One limitation of our work is that we cannot disentangle the contribution to abstinence of the individual components of the intervention. We assume that each is important, but we cannot model their contributions, or whether important interactions exist. It is therefore important to identify the most clinically effective, and cost effective components, to create an intervention that can be delivered in real-world ED settings.

To that end, we propose to study the effect of our intervention components using a new, innovative methodology: the Multiple Optimization Strategy (MOST).¹³⁻¹⁷ The MOST approach, developed by [name] (a consultant on this proposal), is an iterative process that involves testing intervention components in a full- or reduced-factorial design, examining the effects of each, and assembling those components found to be effective within a fixed cost

constraint into a package, which is then tested in a traditional randomized clinical trial. MOST has been particularly useful in designing interventions to treat tobacco dependence.^{17,18}

Hence, the goal of this proposal is to conduct a factorial trial, in the ED, of the 4 key components of our intervention package—motivational interviewing, nicotine replacement therapy (NRT), QL referral and texting. We will then identify the clinically effective components, subject to cost effectiveness and qualitative analyses, and assemble a multicomponent, generalizable package to be tested in a future clinical trial.

3. **Research Plan:** Summarize the study design and research procedures using non-technical language that can be readily understood by someone outside the discipline. **Be sure to distinguish between standard of care vs. research procedures when applicable, and include any flowcharts of visits specifying their individual times and lengths.** Describe the setting in which the research will take place.

RESEARCH STRATEGY:

A. SIGNIFICANCE

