12. Statistical Considerations: Describe the statistical analyses that support the study design. **Analytic strategy: overview.** Intervention components will be analyzed over three domains, as outlined in Figure 2. First, components will be assessed for clinical efficacy, using traditional measures such as biochemically verified tobacco abstinence. If clinically effective, components will then be analyzed for cost-effectiveness and feasibility/acceptability to providers and subjects. For the economic analysis, we will use standard approaches that assess quality-adjusted life years. For the qualitative assessments, we will interview research subjects to assess the feasibility and acceptability of the intervention components. Components that are clinically efficacious, cost-effective, and feasible and acceptable will be retained in the final package, which will be compared to a control condition in a follow-on randomized clinical trial. Analytic tactics are described in detail in the next few sections.

8. Biostatistical considerations. Primary Study Endpoints and Analyses. The primary efficacy endpoint for this study will be biochemically verified 7-day cessation rate at 3 months.⁶⁶ Tobacco use will be assessed by self-report and confirmatory biochemical testing with exhaled carbon monoxide. Patients who assert abstinence by phone interview will be asked to return to hospital for assessment of exhaled carbon monoxide.

Baseline comparability. The adequacy of the randomization will be assessed by comparing the distribution of baseline demographic and clinical characteristics among the intervention groups. Comparability for continuous variables will be examined graphically and by summary statistics,

and categorical variables by calculating frequency distributions. Data analyses will be conducted using SAS 9.3 (SAS Institute, Cary, NC).

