Sample size and power calculations. The goal of this proposal is to identify individual tobacco dependence treatment interventions which show clinical efficacy, subject to constraints of cost effectiveness and acceptability. *As each component is allocated to half the participants, the sample size to detect main effects in a full factorial MOST design is not depending on the number of components evaluated, but rather the smallest clinically important difference between the presence and absence of a component.* In our previous trial, we found a difference of 7.3% in biochemically confirmed abstinence between the control and intervention arms at 3 months. It is reasonable to expect that, in this factorial trial, the effect of individual components will be less than that seen in the multicomponent trial.^{13,69} Therefore, we have chosen an absolute difference of 5% for the main effects of each component. (We considered a narrower absolute difference of 4%, but the sample size and resources needed become unfeasible.) With a two-sided 0.05 significance level, and an average abstinence proportion of 4.9% in the absence of a component, a total sample size of 860 participants will provide 80% power to detect a 5% increase in the abstinence rate. We will enroll **1056** participants to account for up to a 15% dropout rate by 3 months. *Although we will investigate whether the effect of a component is dependent on the levels of other components (i.e. interactions) our trial has not been powered with the intent to detect these interactions.*

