Calculating C/E ratios: We will calculate ICERs in two passes. A naive first pass will array cost and regression-adjusted quit rate for each of the 16 MOST cells, ignoring if differences are statistically significant. This naive look will let us drop clearly dominated cells where higher cost is associated with a lower quit rate, as well as any cells that proved infeasible in the clinical setting or were unacceptable to staff. In a refined pass, we will define incremental component cost effectiveness as $\Delta C/\Delta E$, where ΔC is the cost a component adds and ΔE is the effectiveness associated with the component. This refined look at the remaining candidates will use two effectiveness measures, the 3-month quit rate and the simulated quality-adjusted life year (QALY) gain. A QALY is a standard measure of health-related quality of life, defined so that a year in perfect health is valued at 1.0 and death is valued at 0.0.⁷⁷ Even if one component costs more per quitter than another, it still may be worthwhile if it helps more smokers to quit at an acceptable cost per QALY gained. By estimating QALYs gained per quitter, we get a measure that lets us judge the cost of cessation gains relative to other smoking interventions, with a tentative ceiling of **\$5000** per QALY gained that we will refine in year 4 by updating our literature review on cessation interventions regularly used in medical settings.

The analysis will require estimates of the QALY losses and medical costs averted by smoking cessation. For QALY loss, the most recent estimates⁸¹⁻⁸³ are better than older estimates.^{84,85} For medical costs, we expect to use the latest update to CDC's SAMMEC model¹ which build from the methods pioneered by V. Miller.⁸⁶ We will inflate all cost savings to the same year's dollars as the program costs and compute present value of savings in future years at a 3% discount rate. To account for relapse, we will insert our chosen smoking costs and our observed quit rate pattern into the widely used BENESCO (benefits of smoking cessation on outcomes) Markov simulation model of cessation duration or a closely related model.^{78,79} These models stem from a 2002 World Health Organization model. The resulting estimates will let us answer the question, which efficacious ED-based interventions maximize quits while staying below the acceptable cost per QALY gained.

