To better inform our package choice, we will estimate 95% CIs around the ICERs. To estimate ratio variance, we will start with roughly estimated standard errors or distributional data for each number in the cost-effectiveness equation. We will use bootstrapping simulation

methods that form an empirical probability distribution.⁸⁷ To handle estimates with unknown variance, notably the discount rate, we will conduct sensitivity analyses. The sensitivity analyses examine if different input assumptions would change package selection.

10. Qualitative analysis. The final analytic strategy is a mixed methods analysis of those components found to be clinically efficacious. The goal of this analysis is to ensure that those components are considered feasible, practical, and acceptable by the *patients* who we wish to use the package in real-world settings. Intervention components scoring well in Likert assessments and found feasible and acceptable in interviews with subjects (that are also clinically efficacious and cost-effective) will be retained to study in the future randomized trial.

As we did previously, we will conduct phone interviews with study subjects to assess their views of the components, alone and in combination. Unlike our earlier qualitative work, which focused on the texting component only, we will assess subjects' view of all components in the factorial design: texting, BNI, QL, and NRT. *As before*, Likert-type questions will be included. We will make sure to sample individuals who were randomized to each of these as a single intervention. We will also sample individuals who were in arms where we identify important 2-way or 3-way interactions of efficacy.

We will use a grounded theory approach, in which explanatory theories will emerge from inspection of themes derived from coded transcripts.^{88,89} All interviews will be audiotaped and professionally transcribed. Interviews will be coded by [name] and study personnel with experience in coding. Subjects will be interviewed until thematic saturation is reached. We anticipate this will mean 25-30 subjects. [name] will use ATLAS.ti (ATLAS.ti GmbH).

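### The plan gives two rules for which components receive a cost-effectiveness ratio, and under the stricter one Hypothesis 2 could go unanswered

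*Combined protocol and SAP*

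**What the plan says.** Hypothesis 2 (Section V.1) is "At 3 months, at least 1 intervention will be cost-effective, using a societal perspective". It carries no condition on efficacy.

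On which components are costed, the sections differ:

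- **Section V.12, Analytic strategy: overview.** Efficacy comes first: "If clinically effective, components will then be analyzed for cost-effectiveness and feasibility/acceptability to providers and subjects". A component is retained only if it is efficacious, cost-effective, and feasible and acceptable.
- **9. Economic analysis, Overview.** The purpose is to decide, for each component, whether its benefit justifies its added cost. No efficacy condition is stated.
- **9. Economic analysis, Calculating C/E ratios.** The first pass sets cost against adjusted quit rate for all 16 cells, "ignoring if differences are statistically significant". It removes cells that are dominated, infeasible or unacceptable to staff. The second pass computes cost per quit and per QALY for what remains. No p-value rule appears, but the subsection closes by asking which of the efficacious interventions give the most quits under the acceptable cost per QALY.

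The Background statement, "We will then identify the clinically effective components, subject to cost effectiveness and qualitative analyses", fits either rule.

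On uncertainty, the plan says "To better inform our package choice, we will estimate 95% CIs around the ICERs", by bootstrap. It describes no allowance for selection. No section says how Hypothesis 2 is judged if no component is significant.

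**The concern.** The efficacy test (0.05 per main effect, Analysis for Aim 1) and the effectiveness term of the ratio use the same outcome in the same participants: verified abstinence at 3 months. If only components that pass the test are costed, two things follow.

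First, if none passes, a stated hypothesis has no analysis, although costs are collected by component for all treatment received.

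Second, every reported ratio has a denominator that had to be large enough to reach significance. On average that denominator exceeds the true effect, so cost per quit looks too low. A component with a small, real effect and a low cost gets no published ratio at all.

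If the Economic analysis is followed instead, ratios exist whatever the p-values. An analyst cannot tell from the plan which rule applies, and could choose after seeing the efficacy results.

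**Working it through.** **Inputs from the protocol (Sample size and power calculations; Analysis for Aim 1).** The test is two-sided at 0.05, and 4.9% are taken to be abstinent when the component is absent. On size: "a total sample size of 860 participants will provide 80% power to detect a 5% increase in the abstinence rate". On allocation: "each component is allocated to half the participants". The enrolment target is 1056, so 1056 / 2 = 528 per component level. Missing outcomes count as smoking in the primary analysis, so all 528 enter.

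**The plan's own figure.** Two proportions, pooled variance, no continuity correction, 4.9% against 9.9% (mean 7.4%):

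n per level = [1.96 × √(2 × 0.074 × 0.926) + 0.842 × √(0.049 × 0.951 + 0.099 × 0.901)]² / 0.05² = (0.7256 + 0.3101)² / 0.0025 = 429.1, so 430 per level and 860 in total. The stated figure reproduces.

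**The efficacy screen at 528 per level.** At a 4.9% base rate, the smallest significant difference is about 3.0 points.

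**Assumed smaller effect.** The earlier package, with three of the present components and no texting, gave 7.3 points. An equal split is 7.3 / 3 = 2.43 points. This is an assumption; the documents give no split. With rates of 4.9% and 7.33%:

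- Critical difference: 1.96 × √(2 × 0.0612 × 0.9388 / 528) = 0.0289.
- SE of the difference: √[(0.049 × 0.951 + 0.0733 × 0.9267) / 528] = 0.0147.
- z = (0.0289 − 0.0243) / 0.0147 = 0.31, so the chance of passing is about 0.38.
- Mean estimate given a pass: 0.0243 + 0.0147 × φ(0.31) / 0.38 = 0.0243 + 0.0148 = 0.039. Simulation gives 3.91 points, and 3.91 / 2.43 = 1.61.
- Chance that none of three such components passes, treating the tests as independent: (1 − 0.377)³ = 0.24, using the simulated pass rate of 0.377.

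**Range of true effects.** Simulated two-proportion z tests, 528 per level, 4.9% base rate, significant positive results only. Effects below 5 points are assumptions. The cost-per-quit column is the mean of true effect divided by estimate, with the cost held fixed.

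| True effect (points) | Chance of passing | Mean estimate if passed | Estimate / truth | Cost per quit shown / true |
|---|---|---|---|---|
| 5 | 88% | 5.4 | 1.07 | 0.99 |
| 4 | 73% | 4.7 | 1.17 | 0.90 |
| 3 | 51% | 4.2 | 1.39 | 0.75 |
| 2.43 | 38% | 3.9 | 1.61 | 0.65 |
| 2 | 28% | 3.7 | 1.87 | 0.55 |

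Chance that none of four equally effective components passes, as (1 − pass rate)⁴: below 0.1% at 5 points, 0.5% at 4, 5.6% at 3, 27% at 2.

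The calculation leaves out covariates, the interaction terms in the planned logistic model, and any dilution from missing outcomes.

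**The case against.** The overview is a summary, and it says that the detailed tactics follow. The detailed Economic analysis has no significance filter, so on a fair reading ratios exist even if nothing is significant. This stands. A reader might infer that cost-effectiveness is worked out only for components that pass and that Hypothesis 2 simply has no analysis otherwise. The documents do not support that as a flat statement. It is the consequence of one of two written rules. The overview still states that rule, and the closing question about efficacious interventions echoes it, so the conflict is real.

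A second objection is that retention requires efficacy under either rule, so a component that fails is excluded whatever its ratio. This also stands. The conflict affects what is estimated and reported and how Hypothesis 2 is answered. It does not change which components go forward.

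Third, the trial is designed for 5 points, where selection matters little. That is right at the design effect. But the sample-size section sets 5 points as the difference to detect, after finding 4 unfeasible to study, and expects single components to do less than the 7.3 points of the whole package. Smaller true effects are therefore plausible, though their size is not documented.

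A reader might also turn the understated cost per quit into a cost per QALY and set it against the tentative $5000 ceiling. The documents do not support that conversion. It assumes that cost per QALY varies as the reciprocal of the effect, whereas the plan also brings in averted medical costs and discounted savings.

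**Conclusion.** The concern holds as an inconsistency with a consequence. The overview in Section V.12 makes the cost analysis conditional on efficacy, and the Economic analysis does not.

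If the overview governs, the risk that Hypothesis 2 goes unanswered is negligible when all four components have the 5-point design effect. It is about 24% when three components have 2.4 points each and texting is not counted. The effects behind the reported ratios would be overstated by about 7% at a true 5 points and by about 60% at 2.4 points. The 2.4-point figures rest on an assumed equal split of an earlier result and on the plan's 4.9% base rate.

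If the Economic analysis governs, reporting every ratio introduces no such selection, and Hypothesis 2 has an analysis in every outcome. Even then, the ratio of a retained component is conditional on its significance in the same data.

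**What to change.** Amend the overview in Section V.12 to agree with the Economic analysis:

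1. Estimate and report incremental cost per quit and per QALY, with 95% confidence intervals, for all four components whatever the efficacy p-value. Repeat this under Calculating C/E ratios, because the second pass there is limited to candidates that survive the first.
2. Judge Hypothesis 2 on those four sets of estimates, and say so.
3. Apply the efficacy criterion only when choosing which components to retain.
4. State in the report that the ratios of retained components are conditional on significance in the same data.

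Enrolment, data collection and the primary test do not change, since costs are already to be collected by component. The price is slightly more analysis and some imprecise ratios for non-significant components. The change leaves retention and the ratios of passing components as they were. It removes the gap and the selective reporting, and the note in step 4 tells the reader about the selection that remains.

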Inc. (formerly Alere, Inc.) who is an expert on the use of tobacco quitlines. She has collaborated with [name] on several projects.

D. OVERALL APPROACH

1. Overview. We propose to optimize the identification and treatment of adult smokers seen

Table 2. Arms of the trial.				
Green = condition is offered.				
Red = condition is not.				
Arm	BNI	NRT	QL	Text
1	Green	Green	Green	Green
2	Green	Green	Green	Red
3	Green	Green	Red	Green
4	Green	Green	Red	Red
5	Green	Red	Green	Green
6	Green	Red	Green	Red
7	Green	Red	Red	Green
8	Green	Red	Red	Red
9	Red	Green	Green	Green
10	Red	Green	Green	Red
11	Red	Green	Red	Green
12	Red	Green	Red	Red
13	Red	Red	Green	Green
14	Red	Red	Green	Red
15	Red	Red	Red	Green
16	Red	Red	Red	Red

BNI = Brief Negotiated Interview.
 NRT=Nicotine Replacement Therapy
 QL=Quitline referral
 Text=Smoke-Free Text

in a hospital ED. To do this we will employ the Multiple Optimization Strategy to develop a multicomponent intervention that will consist of some combination of the following: (1) a Brief Negotiation Interview (BNI, a variant of a motivational interview³²), delivered by a trained research assistant; (2) provision of 6 weeks of nicotine patches and gum to the research participant, with application of the first patch in the ED; (3) active referral to the Connecticut Smokers' Quitline; and (4) enrollment in the SmokefreeTXT short-messaging service (SMS) texting program for mobile phones. Using MOST principles, the first phase of the study will use a 2x2x2x2 full-factorial design to identify the components most likely to be efficacious in combination. Although the factorial design requires the allocation of participants to 16 different combinations of the 4 components (Table 1), evaluation of each individual component is performed comparing all of those receiving a component to all of those not receiving a component, making this an efficient design. For instance, evaluation of the BNI component will compare those randomized to arms 1 through 8 to those in arms 9 to 16. The second phase will consist of designing and proposing a 2-arm randomized clinical trial comparing the efficacy of the multicomponent intervention package to usual care; this will be

conducted in a **future** application.

The primary outcome measure is the proportion of smokers in each group abstinent at 3 months (verified by exhaled carbon monoxide). Secondary outcomes include the cost effectiveness of the intervention, as well as acceptability/feasibility. The BNI will be specified in a manual and provided to research assistants (RAs), who will be trained by experienced study personnel. Patients will be screened for eligibility and enrolled by these RAs, with the proviso that the RA who enrolls a participant will not be the RA who performs the BNI.

2. Setting. New Haven, Connecticut, is a poor city; 24.4% of its 350,000 residents live in poverty. YNHH is a tertiary care center. In 2013, women represented approximately 55% of the ED population; the mean age of ED adults was 41 years. The racial mix of our patients reflects that of New Haven: 65% White, not Hispanic; 23% African-American, not Hispanic, 10% Hispanic; 2% other. Payor status for ED smokers is approximately 55% Medicaid, 5% Medicare, 30% private insurance, and 10% self-pay.

Number of smokers. Based on work from prior studies at the YNHH ED, and assuming a conservative prevalence rate of smoking (at least 5 cigarettes/day) of 20% among uninsured or Medicaid patients, we estimate the YNHH ED treats 15,200 potentially eligible patients annually. (This estimate is conservative because low-income individuals smoke more than others. Data from the 2006 National Health Interview Survey found a smoking prevalence rate of 30.6%

among individuals with household incomes below the federal poverty level, compared to 20.4% for those with household incomes above the poverty level.⁴⁵⁾

3. Participants. Inclusion criteria. Patients who present to the adult ED at Yale-New Haven Hospital (YNHH) will be eligible for the study if they are: (1) 18 years or older (2) have smoked \geq 100 cigarettes lifetime (3) describe themselves as every or some day smokers (4) smoke at least 5 cigarettes/day (5) own a cellphone with texting capability, and (6) are able to give written informed consent (a draft is in the Appendix).

Exclusion criteria. Patients will be excluded for: (1) Inability to read or understand English; (2) currently receiving formal tobacco dependence treatment; (3) life-threatening or unstable medical, surgical, or psychobehavioral condition; (4) unable to provide at least one collateral contact; (5) live out-of-state; (6) leaving the ED against medical advice (7) *being pregnant (self-report or urine testing)*, nursing, or trying to conceive.

4. Entry into study and Randomization. *Subjects will be recruited during all days of the week, from 7a-11p.* Potential subjects will meet with a research assistant (RA) to be evaluated for eligibility. Patients will be asked for verbal consent to complete the 2-item tobacco screener used by the Behavioral Risk Factor Surveillance System (Do you currently smoke every day, some days, or not at all? Have you had more than 100 cigarettes in your lifetime?). Patients who report smoking $<$ 5 cigarettes/day will not be enrolled, but will be given a handout recommending that they abstain from smoking, contact their primary care provider, and consider calling the quitline. Individuals *who meet* inclusion and exclusion criteria and consent to participate will have their baseline assessments performed, and then will be randomized to one of 16 combinations of components (Table 1). To assure equal intervention allocation and concealment of intervention allocation a random permuted block sequence will be generated and intervention assignments distributed through the clinical trial management system.

5. Components of the Intervention. Our previous work employed a multicomponent approach to ED-initiated tobacco treatment, which used both pharmacologic and behavioral approaches. All components are evidence-based, and cited in the 2008 PHS clinical practice guideline, with the exception of the newest approach, SMS texting. Below we discuss these components, the rationale for each, and supportive evidence. Our intent is to use the MOST approach to identify the individual contributions of these components, and assemble them into an intervention that is effective, efficient, and scalable.

Brief negotiated interview (BNI). Brief Negotiated Intervention (BNI) is a manual-guided therapy that is designed to be feasible in the ED setting. The BNI manual for this study is based on one that we used in our previous trial. The purpose of the BNI is to assist patients in recognizing and changing their tobacco use. It combines techniques based on motivational interviewing and a stage-model of change.^{32,46} The main goals of the interview are to decrease subjects' ambivalence about engaging in tobacco dependence treatment and accepting ED-initiated treatment, including NRT, texting, and QL referral.

The BNI will be delivered by a trained research assistant (RA), a bachelor's-level individual, who will audiotape the encounters. Tapes will be reviewed biweekly by the RAs and [name], to assess fidelity to protocol. In our prior work, the BNIs average 10-15 minutes in length. RAs will receive 10 hours of training by [name] in our manualized BNI, and by [name] in nicotine replacement pharmacotherapy. Next, RAs will role-play patient scenarios with [name], followed by 1 week of shadowing an experienced RA performing BNIs on ED patients. We have used these procedures in all prior studies of ED SBIRT.

If, during the BNI or other interactions, the subject discloses to the RA risky behaviors such as suicidality, intimate partner violence, or use of other substances, the RA will notify the treating ED physician.

Nicotine gum and patch, with initial dose applied in the ED. Subjects randomized to NRT will receive 6 weeks of patches (42 count) and gum (300 pieces of 2mg), free of charge. *All NRT will be given to the subject in a small shopping bag.* NRT dosing is tailored to the patient's score on the Heavy Smoking Index.⁴⁷ Patches come in 7, 14 and 21 mg doses. The first patch is applied by an ED nurse during the index visit. This allows us to demonstrate to the subject how to use the patch, its ease of use, and acceptability. It does bypass the traditional model of setting a quit date, although subjects may continue to reduce their tobacco use while using NRT. In our previous study, this approach was accepted enthusiastically by subjects. We employ combination NRT because of its generally greater efficacy than NRT monotherapy in promoting tobacco abstinence.⁴⁸

